## Document History

Document	Version Date
Amendment 2	09 Feb 2023
Amendment 1	23 Jun 2022
Original protocol	25 Mar 2022

This amendment incorporates all revisions to date, including amendments made at the request of country health authorities and IRBs/ECs and any protocol administrative change letter(s).

## Protocol Amendment Summary of Changes Table

### Amendment 2 (09 Feb 2023)

**Overall Rationale for the Amendment:** To add additional blood to plasma ratio sample either on Day 3 or Day 4 or Day 5 in Cohort 1 and on Day 1 in Cohort 2; and to provide additional clarification on blood to plasma ratio sample processing.

Section # and Name	Description of Change	Brief Rationale	Substantial or Nonsubstantial
Title page	Added EudraCT number and ClinicalTrials.gov ID	EudraCT number and ClinicalTrials.gov ID are now available for this study.	Nonsubstantial
Section 1.3. Schedule of Activities – PK Sampling Schemas 1-12; Section 8.5.3 PK Samples for Analysis of PF-07321332 (nirmatrelvir) and Ritonavir; Section 8.5.4. Blood to Plasma Ratio Analysis of PF-07321332 (nirmatrelvir) and ritonavir	Updates to implement collection of 1 additional blood to plasma ratio sample at steady state. Flexibility to collect the sample on a different day if a sample was missed.	This additional blood to plasma ratio sample will help in providing accurate normalization for Tasso PK when compared with nirmatrelvir/ritonavir plasma concentrations.	Substantial
Section 9.4 Interim Analysis	Added text for unblinded reviews of the data	Added text based on text in SAP.	Nonsubstantial

Section # and Name	Description of Change	Brief Rationale	Substantial or Nonsubstantial
Title page	Added EudraCT number and ClinicalTrials.gov ID	EudraCT number and ClinicalTrials.gov ID are now available for this study.	Nonsubstantial
Section 1.3 SoA; Section 10.2. Clinical Laboratory Tests, Table 3; Section 10.9.1. Country Specific Requirements	HIV test at screening added to the laboratory assessments for participants in Germany.	The German Health Authority has requested for all participants to be enrolled in Germany to undergo HIV testing at screening. Participants who do not consent to the screening HIV test will not be able to participate in the study.	Nonsubstantial

## 1. PROTOCOL SUMMARY

### 1.1. Synopsis

#### Protocol Title:

A Phase 1, Open-Label, Non-Randomized Study to Investigate the Safety and PK Following Multiple Oral Doses of PF-07321332 (Nirmatrelvir)/Ritonavir in Adult Participants with COVID-19 and Severe Renal Impairment Either on Hemodialysis or not on Hemodialysis.

**Brief Title:** A Phase 1, Open-label, Non-randomized Safety and PK Study of Multiple Oral Doses of PF-07321332 (Nirmatrelvir)/Ritonavir in Adult Participants with COVID-19 and Severe Renal Impairment.

#### Regulatory Agency Identification Number(s):

US IND Number:	153517
EudraCT Number:	NA
ClinicalTrials.gov ID:	NCT05487040
Pediatric Investigational Plan Number:	NA
Protocol Number:	C4671028
Phase:	1

#### Rationale:

The purpose of this study is to evaluate the safety and PK of PF-07321332 (nirmatrelvir)/ritonavir in adults with severe renal impairment and COVID-19. Eligible participants include those with severe renal impairment (defined as eGFR <30 mL/min/1.73 m^2) and not yet receiving HD (Cohort 1) and individuals receiving HD (Cohort 2).

#### Objectives, Endpoints, and Estimands:

Objectives	Endpoints	Estimands
Primary:	Primary:	Primary:

To describe the safety and tolerability of PF-07321332 (nirmatrelvir)/ritonavir in adult participants with COVID-19 and severe renal impairment.

	

• Incidence of TEAEs.

• Incidence of SAEs and AEs leading to discontinuations.

	

• Not Applicable.

Objectives	Endpoints	Estimands
Secondary:	Secondary:	Secondary:

• To evaluate the effect of severe renal impairment on the PK of PF-07321332 (nirmatrelvir) in participants not on HD.

• To evaluate the effect of severe renal impairment on the PK of PF-07321332 (nirmatrelvir) in participants on HD.

	

• Plasma PF-07321332 (nirmatrelvir) PK parameters including <math>C_{max}</math>, <math>CL/F</math>, <math>Vz/F</math>, <math>AUC_{0-\tau}</math>, <math>t_{1/2}</math>, and <math>C_{trough}</math> estimated from the population PK model.

	

• Not Applicable.

• To evaluate the effect of HD on the PK of PF-07321332 (nirmatrelvir).

	

• HD clearance (CLd) of PF-07321332 (nirmatrelvir).

• Fraction of PF-07321332 (nirmatrelvir) dose removed from the body by dialysis (Fd).

	

• Not Applicable.

### Overall Design:

This is a Phase 1, open-label study to evaluate the effect of severe renal impairment on the PK of PF-07321332 (nirmatrelvir)/ritonavir and the safety and tolerability of PF-07321332 (nirmatrelvir)/ritonavir in non-hospitalized adult participants with COVID-19 and severe renal impairment and not yet receiving intermittent HD (Cohort 1) and severe renal impairment receiving intermittent HD (Cohort 2). The study will be conducted in 2 parallel cohorts. Cohort 1 will enroll eligible participants with severe renal impairment (defined as eGFR <30 mL/min/1.73 m^2) and not on HD. Cohort 2 will enroll eligible participants with severe renal impairment and on HD. All eligible participants will be assigned to receive a single dose of PF-07321332 (nirmatrelvir)/ritonavir 300 mg/100 mg orally on Day 1 followed by PF-07321332 (nirmatrelvir)/ritonavir 150 mg/100 mg QD from Day 2 to Day 5. Population PK model-based simulations showed that the PF-07321332 (nirmatrelvir) single dose of 300 mg on Day 1 followed by 150 mg of PF-07321332 (nirmatrelvir) QD on Day 2 to Day 5 with ritonavir 100 mg in severe renal impaired participants gives comparable exposure ( $AUC_{0-24}$  and  $C_{max}$ ) to COVID-19 patients with normal renal function at the 300 mg PF-07321332 (nirmatrelvir)/ 100 mg ritonavir BID dose for 5 days. Published reports and internal data (C4671011 data on file) show ritonavir PK is comparable between normal healthy participants and severe renal impairment patients and only small fraction of ritonavir dose is removed by HD. Ritonavir 100 mg QD or BID dose has been used for several protease inhibitors (eg, darunavir) with small difference in dose normalized  $C_{trough}$  of protease inhibitors. Additionally, the PK of PF-07321332 (nirmatrelvir) with 100 mg QD of ritonavir in severe renal impairment participants is expected to be similar to those of healthy

participants taking 100 mg BID of ritonavir. Therefore, the ritonavir dose of 100 mg QD was selected for this study.

This study will use the program-level E-DMC which is independent of the study team and includes only external members, and is responsible for the ongoing monitoring of the efficacy and safety of participants in the program's studies according to the E-DMC charter ([Section 10.1.5.1](#)).

### **Number of Participants:**

Approximately 24 participants (12 participants in Cohort 1 and 12 participants in Cohort 2) will be assigned to study intervention.

Note: "Enrolled" means a participant's, or their legally authorized representative's, agreement to participate in a clinical study following completion of the informed consent process and assignment to study intervention. A participant will be considered enrolled if the informed consent is not withdrawn prior to participating in any study activity. Potential participants who are screened for the purpose of determining eligibility for the study, but do not participate in the study, are not considered enrolled.

### **Study Population:**

Inclusion and exclusion criteria are listed below:

#### **Inclusion Criteria**

Participants must meet the following inclusion criteria to be eligible for enrollment into the study:

#### **Age and Sex:**

1. Participants  $\geq 18$  years of age (or the minimum country specific age of consent if  $>18$ ) at the time of the Screening Visit.
  - WOCBP may be enrolled.
  - WOCBP must agree to use an effective method of contraception described in [Section 5.3](#). Refer to [Appendix 4](#) for reproductive criteria for male and female participants.

#### **Disease Characteristics:**

2. Mild-to-moderate COVID-19 disease as defined in [Appendix 9](#) with confirmed SARS-CoV-2 infection in any specimen collected within 5 days prior to treatment assignment.

Note: RT-PCR is the preferred method; however, with evolving approaches to confirmation of SARS-CoV-2 infection, other molecular or antigen tests that detect viral RNA or protein are allowed. The test result must be available to confirm eligibility. Participants may be enrolled based on positive results of a rapid SARS-CoV-2 antigen test performed at screening.

3. Initial onset of signs/symptoms attributable to COVID-19 within 5 days prior to the day of treatment assignment.

#### **Other Inclusion Criteria:**

4. Participants who are willing and able to comply with all scheduled visits, treatment plan, laboratory tests, lifestyle considerations, and other study procedures.

#### **Additional Inclusion Criteria for Cohort 1 (Severe Renally Impaired and not on HD):**

5. Severe renal impairment defined as eGFR <30 mL/min/1.73m^2 (using the 2021 CKD-EPI serum creatinine only eGFR formula in Section 10.7.2.1) measured by clinical laboratory testing on at least 2 occasions, one of which must be within 3 months of Screening and not receiving intermittent HD treatments.

#### **Additional Inclusion Criteria for Cohort 2 (Receiving HD):**

6. Receiving stable intermittent HD for at least 6 weeks prior to Screening.

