Pregnancy test ( $\beta$ -hCG)	X						X	X	
 
• A negative urine pregnancy test must be confirmed at screening and prior to dispensing treatment for all WOCBP. Pregnancy tests will also be done whenever 1 menstrual cycle is missed during the active treatment period (or when potential pregnancy is otherwise suspected) and at Day 34 ±3 or ET visit.
 
• Local urine testing (ie, at the site, home, etc) will be standard for the protocol unless serum testing is required by local regulation or IRB/EC or the participant is anuric.
 
• See Section 8.3.5, Appendix 2 and Appendix 4.
 

HIV test (Germany only)	X								
 
• Local HIV testing at screening will be performed for participants in Germany as required by the German HA.
 
• See Appendix 2 and Appendix 9.
 

Rapid antigen testing	X								
 
• Only required if a participant does not have results of a positive SARS-CoV-2 test that was obtained within 5 days prior treatment assignment.
 
• See Section 5.1.
 

CCI									

PFIZER CONFIDENTIAL

Visit Identifier	Screening	Baseline (Day 1)	Day 5	Day 10	Day 14	Day 21	Day 34	ET	Notes
Visit Window	Day -1 to Day 1	0 days	0 days	±1 day	±2 days	±2 days	±3 days		
Type of Visit	In-Person Site or Home Health Visit with Telehealth	In-Person Site Visit	In-Person Site or Home Health Visit	Telehealth Visit	In-Person Site, Home Health or Telehealth Visit	Telehealth Visit	In-Person Site, Home Health or Telehealth Visit	In-Person Site, Home Health or Telehealth Visit	
Specified biomarker research (plasma)		X	X		[X]		[X]	[X]	
CCI
 
 
Samples will be collected at Day 1 and Day 5 for all participants.
 
If an in-person (site or home health) visit is conducted, this sample should be collected at Day 14 ±2 days, Day 34 ±3 days and ET visits.
 
See Section 8.7.2.1.
 

Retained Research Samples for biomarkers (Prep B2.5)		X	X		[X]		[X]	[X]	
 
Samples will be collected at Day 1 and Day 5 for all participants.
 
See Section 8.7.3.
 
If an in-person (site or home health) visit is conducted, this sample should be collected at Day 14 ±2 days, Day 34 ±3 days or ET visits.
 

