Study C4671002 (NCT05011513), is a Phase 2/3, randomized, double-blind, placebo controlled study in non-hospitalized symptomatic adults with low risk of progression to severe illness. A prespecified interim analysis of Study C4671002, which included 45% of the trial's planned enrollment, showed that the novel primary endpoint of self-reported, sustained alleviation of all symptoms for 4 consecutive days, for PF-07321332 (nirmatrelvir)/ritonavir compared to placebo, was not met. The key secondary endpoint of COVID-19-related hospitalization or death from any cause through Day 28 was also examined at the interim analysis, showing 0.6% of those who received PF-07321332 (nirmatrelvir)/ritonavir were hospitalized following randomization (2 of 333 hospitalized with no deaths), compared to 2.4% of participants who received placebo and were hospitalized (8 of 329 hospitalized with no deaths).

A Phase 1, open label, 2-part study (C4671011) to investigate the effect of stable mild (eGFR  $\geq 60$  to  $< 90$  mL/min), moderate (eGFR  $\geq 30$  to  $< 60$  mL/min), or severe (eGFR  $< 30$  mL/min and not requiring dialysis) renal impairment on the plasma and urine PK, safety, and tolerability of PF-07321332 (nirmatrelvir) has been completed. PF-07321332 (nirmatrelvir) systemic exposure increased with increasing severity of renal impairment.

Following a single 100 mg dose of PF-07321332 (nirmatrelvir) administered orally in combination with ritonavir 100 mg dose given at four scheduled time points relative to the single dose, the adjusted geometric mean (90% CI) AUCinf, test/reference ratios for renal

impairment (test) compared to normal renal function (reference) were 123.8 % (99.6%, 153.9%) for mild renal impairment, 187.4% (148.5%, 236.5%) for moderate renal impairment, and 304.49% (237.6%, 390.2%) for severe renal impairment. Adjusted geometric mean (90% CI) test/reference ratios for  $C_{max}$  were 129.78% (101.9%, 165.3%) for mild renal impairment, 138.1% (113.2%, 168.6%) for moderate renal impairment, and 148.0% (111.4%, 196.7%) for severe renal impairment participants. Regression plot of CL/F versus eGFR derived from CKD-EPI equation showed a clear trend of decreasing clearance with a decrease in renal function, with intercept of 1.83 ( $P = 0.0009$ ) and slope of 0.05 ( $P < 0.0001$ ).

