**Table 3. Protocol-Required Safety Laboratory Assessments**

Hematology	Chemistry	Other	Additional Tests
Hemoglobin	Urea and creatinine	Pregnancy test	For suspected DICI/DIKI:
Hematocrit	CystatinC and eGFR	( $\beta$ -hCG) a	Creatinine (Scr)
RBC count	Glucose	SARS-CoV-2 serology	CystatinC (Scys)
Platelet count	Calcium	(IgG and IgM)	eGFR (Scr only and combined
WBC count	Sodium	HIV Testing b	Scr+Scys)
Total neutrophils (Abs)	Potassium		Spot (dipstick) UACR
Eosinophils (Abs)	Chloride		Needed for Hy's Law
Monocytes (Abs)	Total CO 2 (bicarbonate)		AST, ALT (repeat)
Basophils (Abs)	AST, ALT		Total bilirubin (repeat)
Lymphocytes (Abs)	Total bilirubin		Albumin
	Alkaline phosphatase		Alkaline phosphatase (repeat)
	Albumin		Direct bilirubin
	Total protein		Indirect bilirubin
			Creatine kinase
			GGT
			PT/INR
			Total bile acids
			Acetaminophen drug and/or
			protein adduct levels
			Hepatitis serology

- a. Local urine testing using the central lab-provided test (locally purchased test is acceptable after Day 1 if the participant and/or home health staff does not have one provided by the central lab) will be standard for the protocol unless serum testing is required by local regulation or IRB/EC or the participant is anuric. A negative urine or serum ( $\beta$ -hCG) pregnancy test must be confirmed at screening and prior to dispensing treatment for ALL WOCBP.
- b. Local HIV testing at screening will be performed for participants in Germany as required by the German HA.

The investigator must review the laboratory report, document this review, and record any clinically relevant changes occurring during the study in the AE section of the CRF.

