### **10.7.3. Adverse Event Grading for Kidney Safety Laboratory Abnormalities**

AE grading for decline in kidney function (ie, eGFR or eCrCl) will be according to KDIGO criteria.

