6.6.2. Laboratory Data

Lab data and the corresponding changes from baseline will be summarized over time (Day 1, 5) by cohort, and overall using standard descriptive statistics. Any abnormalities of potential clinical concern according to the criteria specified by the Pfizer reporting standards will be described. Data will be presented in tabular and/or graphical format, as appropriate.

Data collected at screening that are used for inclusion/exclusion criteria will be considered source data, and will not be required to be reported, unless otherwise noted.

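### eGFR and its Day 1 to Day 5 change are summarised and graded in dialysed participants with no exemption, so the Cohort 2 and pooled figures can reflect dialysis timing and not kidney function

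*Protocol*

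**What the plan says.** **Who is in Cohort 2.** The design text in the synopsis says "Cohort 2 will enroll eligible participants with severe renal impairment and on HD". The criterion that puts this into practice is "Receiving stable intermittent HD for at least 6 weeks prior to Screening"; it sets no eGFR, urine-output or residual-function condition. The creatinine-based definition ("using the 2021 CKD-EPI serum creatinine only eGFR formula in Section 10.7.2.1") belongs to Cohort 1 eligibility.

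**What is measured.** Protocol Table 3 lists urea and creatinine, and also "CystatinC and eGFR", as required chemistry with no cohort restriction. SAP Table 6 keeps urea, creatinine and eGFR but drops cystatin C. The Schedule of Activities draws chemistry from all participants on Day 1 and Day 5.

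**What is reported.** SAP 3.4 makes laboratory values baseline variables. SAP 6.6.2 states: "Lab data and the corresponding changes from baseline will be summarized over time (Day 1, 5) by cohort, and overall". It exempts screening data used for eligibility, but not the Day 1 or Day 5 eGFR.

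**What is graded.** Protocol 10.7.3 states: "AE grading for decline in kidney function (ie, eGFR or eCrCl) will be according to KDIGO" criteria. No cohort is excepted.

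**Timing.** The Schedule of Activities requires baseline laboratory samples before the first dose. When Day 1 is an HD day, the dose follows the session, so the baseline sample may be drawn before or after HD. No rule ties the Day 1 or Day 5 draw to the session.

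**The concern.** An eGFR computed from serum creatinine moves whenever creatinine moves. In a participant on intermittent HD, a session can lower creatinine without any change in the kidneys. If the two draws fall at different points of the dialysis cycle, the change from baseline contains that difference.

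The table would present it as a change in kidney function in a safety report on people with severe renal impairment. With 12 participants planned per cohort, Cohort 2 supplies 12/24 = 50% of the overall column, so the artefact also reaches the pooled row. Grading eGFR decline on the same values adds a route to spurious grades.

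A smaller matter sits beside this. The protocol's Clinical Overview reports "a clear trend of decreasing clearance with a decrease in renal function", but nothing in the visible plan records residual kidney function in Cohort 2. Sites must already know who is anuric for one purpose: urine pregnancy testing applies "unless serum testing is required by local regulation or IRB/EC or the participant is anuric".

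**Working it through.** **1. The plan's own precision figure.** Half-width = t(0.95, n-1) x CV / sqrt(n). With n = 12 and CV = 0.4: 1.796 x 0.4 / 3.464 = 20.7%, so the 90% CI runs from 79.3% to 120.7%, with width 41.47% against the stated 41.4%. It reproduces and is not in dispute; step 5 uses it.

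**2. HD status on the two laboratory days** (protocol PK Sampling Schemas 2-12):

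| Schemas | Day 1 | Day 5 |
|---|---|---|
| 2, 3 | HD | HD |
| 4, 5, 6, 7 | HD | no HD |
| 8, 9, 10 | no HD | no HD |
| 11, 12 | no HD | HD |

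Status differs in 4 + 2 = 6 of 11. Schemas 2 and 3 are not protected either: both days are HD days, and each sample may be drawn before or after the session.

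**3. Sensitivity of creatinine-only eGFR** (protocol 10.7.2.1; creatinine above the knot, exponent -1.200). The ratio of eGFR after to before a session is (1 - r)^-1.2, where r is the fractional fall in creatinine. Both r and the pre-session creatinine below are assumptions. Example: a man aged 60 with pre-session creatinine 8 mg/dL, eGFR = 142 x (Scr/0.9)^-1.2 x 0.9938^60.

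| r | Scr after (mg/dL) | eGFR before | eGFR after | Ratio |
|---|---|---|---|---|
| 50% | 4.0 | 7.1 | 16.3 | 2.3 |
| 60% | 3.2 | 7.1 | 21.3 | 3.0 |
| 70% | 2.4 | 7.1 | 30.1 | 4.2 |

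In reverse, a baseline drawn just after HD and a follow-up drawn just before HD show an apparent decline of 1 - 0.5^1.2 = 56% to 1 - 0.3^1.2 = 76%. These are the extremes of the cycle; draws at other times give smaller shifts.

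**4. The combined equation.** Its creatinine exponent above the knot is -0.544. If cystatin C did not move at all (an assumption), the same falls would shift eGFR by 0.5^-0.544 = 1.46 to 0.3^-0.544 = 1.93. The timing effect shrinks but remains. The SAP does not say which equation fills its eGFR row.

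**5. Residual function and the PK results.** The regression in protocol 2.2.1 is CL/F = 1.83 + 0.05 x eGFR. Units are not stated; L/h fits 100 mg / 44,040 ng*h/mL = 2.27 L/h. The severe group in that study did not require dialysis, so its use here is illustrative. Residual GFR of 0, 5, 10 and 15 mL/min (assumed) gives CL/F of 1.83, 2.08, 2.33 and 2.58, that is +14%, +27% and +41% over zero.

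For the cohort mean, let residual GFR be uniform from 0 to G. The added CV is (0.05 x G / sqrt(12)) / (1.83 + 0.025 x G). Combined in quadrature with the CV of 0.38 that Table 1 gives for Cmax, at n = 12:

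| G | Added CV | Total CV | 90% CI width |
|---|---|---|---|
| none | - | 0.38 | 39.40% |
| 5 | 3.7% | 0.3818 | 39.59% |
| 10 | 6.9% | 0.3863 | 40.05% |
| 15 | 9.8% | 0.3925 | 40.69% |

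The width grows by about 0.2 to 1.3 points. Residual function can matter for explaining one participant's clearance; it barely affects the precision of the cohort mean.

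**The case against.** The strongest reply is that eGFR is one row of a safety panel. It is not a primary or secondary endpoint, not a Cohort 2 entry criterion, and not an input to CLd or Fd, which SAP 6.2.2 and 6.2.3 calculate from dialyzer concentrations, blood flow, hematocrit and the AUC over the session. That is correct and limits the importance of the point.

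A second reply is that the 2.3- to 4.2-fold shift rests on an assumed creatinine fall and on draws just before and just after a session. That also stands: the shift is possible under the plan as written, not predicted for every participant.

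A third is that grading does not turn every eGFR change into an adverse event. Protocol 8.3.4 and 10.3.1 leave out findings tied to the underlying disease unless judged more severe than expected. This may prevent false events, but it does not correct the summary tables.

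Three stronger readings are tempting, and the documents do not support them:

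- A reader might infer that creatinine-based eGFR is the only kidney marker planned for Cohort 2. Protocol Table 3 also lists urea and cystatin C, and 10.7.2.1 gives a combined equation. None of these measures residual clearance.
- A reader might infer that Cohort 2 clearance is misestimated or the secondary PK objective undermined. Total CL/F is estimated from concentrations, so not measuring residual function does not by itself bias it.
- A reader might infer that this eGFR will be the renal covariate for Cohort 2 in the population PK model. Protocol 9.3.3 and SAP 6.2.1 leave the model to a separate plan, so this cannot be determined.

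**Conclusion.** The point holds for the display and grading of eGFR. Followed as written, the plan produces a Cohort 2 change from baseline, and a pooled change, that can be an artefact of when samples fell in the dialysis cycle. The design makes mixed dialysis states likely, because 6 of 11 schemas differ in HD status between the two days. The possible size is 2.3- to 4.2-fold for creatinine-only eGFR, conditional on an assumed 50-70% creatinine fall per session.

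The documents do not say that eGFR is invalid on dialysis, so calling the reported value false would go too far. What they support is that it is sensitive to HD timing and cannot be read as kidney function without that timing. They do not reproduce the KDIGO thresholds, so which grade a given fall would trigger is left open.

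Unmeasured residual function is a limitation when explaining differences in CL/F between Cohort 2 participants, and no more than that. Redacted text and the content of the HD case report form could not be checked.

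**What to change.** - **SAP 3.4, 6.6.2 and Table 6:** summarise eGFR and its change from baseline for Cohort 1 only, with no overall column. List Cohort 2 values with the sampling time relative to the HD session.
- **Protocol 10.7.3:** limit eGFR-based grading to Cohort 1.
- **Protocol Table 3 and SAP Table 6:** reconcile cystatin C, and state which equation supplies the reported eGFR.
- **Minor addition:** record anuric yes/no and usual daily urine volume in the Cohort 2 history, or state unmeasured residual function as a limitation when between-participant CL/F is discussed.

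The cost is wording in the SAP and one protocol appendix, the sampling time relative to HD in a listing, and at most two history items. No new sample or visit is needed. The downside is that Cohort 2 eGFR is no longer tabulated, and reported urine volume is a crude measure.
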